**Materials and method**

The perception of an implant restoration as esthetic is often attributable to the soft-tissue architecture that frames the clinical crown. (1) In order for an implant-supported restoration to accurately mimic its adjacent natural counterpart, the restorative complex must traverse the soft tissues, transitioning from a cylindrical implant interface to an anatomic configuration determined by the clinical crown. (2) Thus, it has been recognized that the transitional contour design, and any subtle changes to this transmucosal parameter, can have significant effects on the profile of the peri-implant gingival architecture. (3)

Atlantis™ CAD/CAM custom abutments currently offer four design parameters for the degree of lateral angulation of the transition zone from the head of the implant to the restorative margin. Various displacement options of the soft tissues on a primary plane (degree of divergence) can be chosen. However, less flexibility is offered to the clinician regarding modification of secondary planes along the primary plane (i.e., concavities or convexities). Such limitations are currently being addressed utilizing the Atlantis™ “Option 5” or “EPS” (Emergence Profile System) design parameter, which is still in beta mode and not disclosed publicly.

The concept of whether secondary planes along the existing primary plane can aid in enhancement of the peri-implant soft-tissue response remains ill-defined in the current literature and therefore has yet to be adequately addressed. In a recent pilot study (4), a total of 54 implants with an internal connection and an experimental abutment containing a concave, inwardly narrowed profile at the transmucosal level were delivered to 40 consecutive patients. The implant sites were in esthetically demanding areas, the majority (n=43) were placed in the anterior maxillary region. Patients were monitored clinically and via digital photography at abutment placement, and 1, 3, 6, and 12 months post-abutment delivery to assess soft-tissue zenith levels on the mid-facial aspect of the implant restorations. Rompen and colleagues found that in contrast to previous cited reports of 0.6 to 1.5mm of mid-facial soft tissue recession at 1 year (5-7), the experimental concave abutments yielded soft tissue stability, and for the majority of cases observed, soft tissue gain at the mid-facial aspect of the implant site. The

study reported seven implant fixtures (13.0%) displaying mid facial recession of <0.5mm at 12 months, and 29 patients (53.7%) exhibiting a vertical gain of keratinized soft-tissue from baseline to 12 months. No implant sites demonstrated recession of >0.5mm at 12 months. Thus, a statistically significant gain in keratinized soft tissue on the mid-facial aspect of the experimental abutments with inwardly narrowed profiles at the transmucosal level was observed. The authors attributed the gain in keratinized soft tissue height to three principle factors afforded by the abutment's concave secondary plane:

1. The circumferential concavity created a profile that enabled a localized thickening of the soft-tissues to occur, relative to a divergent abutment.
2. The curved concave profile allowed for an increase in length of the soft tissue-to-abutment interface, meaning that a greater biological seal could be obtained for the same vertical height of the implant platform relative to the gingival margin.
3. The circumferential concavity enabled a greater amount of connective tissue attachment to form, enabling a more robust seal to be established.

In a 2009 study, Redemagni et. al (8) examined 28 patients treated with 33 XiVE implant fixtures restored with concave facial emergence profile abutments in the anterior maxillary region for a mean of 20.4 months. For this study population, a mean of 0.0mm (range of -0.5mm to +1.0mm) of labial mucosal recession was observed. The authors' observations agreed with Rompen's findings that concave facial emergence designs were consistent with facial soft tissue stability, most likely due to increased connective tissue volume in the apical transition zone.

Kim and colleagues (9) investigated the influence of the configuration of the surface topography of the transmucosal portion of three commercially available one-piece implant systems in a beagle dog model. The three systems were represented by 1) a flared, machined transmucosal profile (FM group), 2) a concave, machined transmucosal profile (CMG group), and 3) a straight, anodic oxidized surface (SA group). Mandibular premolars (P1-P4) were extracted, and 1 month after extraction, three implants (one of each type) were placed in alternating orders in each beagle's hemimandible, with 4.0mm between each implant type. After 6 months of function, the dogs were sacrificed, and histologic analysis was performed (Fig. 1). The study demonstrated that despite all three implant designs displaying the same biologic widths histologically, the concave (CMG) transmucosal profile displayed the greatest amount of connective tissue contact ( $0.92\text{mm} \pm 0.36\text{mm}$ ) as compared to the flared (FM) transmucosal profile ( $0.39\text{mm} \pm 0.25\text{mm}$ ) and straight (SA) transmucosal profile ( $0.63\text{mm} \pm 0.34\text{mm}$ ).

The above three studies, each unique in their design, have inherent limitations that prevent widespread acceptance and adoption of these concepts. For both the Rompen (4) and Redemagni (8) studies, there was no control cohort group by which to compare the effects of the concave facial abutment profile. As well, the Rompen study did not use standardized photography to obtain precise measurements of the mid-facial gingiva, which induces potential error over multiple follow-up time points. The Redemagni study was retrospective in analysis, and connective tissue grafts were placed on the facial aspect of the implant fixtures at the same time as implant provisionalization. This treatment factor introduces an additional variable that complicates the analysis due to multiple co-variables being present simultaneously. The beagle dog evaluation by Kim (9) is the first histological evidence in support of the concept of concave abutment profiles, but further clinical evaluation in human subjects is needed.

Therefore, we hypothesize that a well designed, randomized clinical trial comparing divergent to concave abutments in controlled clinical conditions should be pursued to investigate whether this proof-of-principle is demonstrable.

The investigators thus proposes to conduct a randomized, prospective, controlled clinical trial comparing the facial gingival profiles around Atlantis™ abutments that have either a linear "divergent" or "concave" transitional profile on the facial and proximal aspect of the abutments (Fig. 2).

Sixty study subjects requiring replacement of a single-rooted tooth with an implant-supported restoration will be recruited. To facilitate recruitment, subjects participating in a funded, randomized, controlled clinical trial at The University of Iowa College of Dentistry on the efficacy of alveolar ridge preservation ([name] – Principal Investigator) will be invited to participate in the proposed study (Fig. 5). Neither implant placement nor restorative therapy will be provided for the 60 subjects participating in the ridge-preservation study.

The authors propose the placement of Osseospeed™ Plus implant fixtures for all 60 subjects, and Uni healing abutments to minimize lateral tissue displacement during healing. After implant placement, but before final impressions are obtained (8 weeks post-placement), subjects will be randomized to either a "divergent" or a "concave" transmucosal abutment design. For fabrication of the experimental abutment, Atlantis™ engineers will initially design a control "divergent" prototype that will be modified with a concavity on the facial and proximal transition zones to obtain an abutment that will otherwise retain all the features of the control abutment. Engineers will measure the linear topographical changes ( $\Delta L = L_c - L_d$ ) of the transition zone, as well as the volumetric change ( $x$ ) on the mid-facial aspect of the abutment induced by the formation of a submucosal concavity (Fig. 2). The primary outcome of the study will be the apico-coronal change of the peri-implant mucosal zenith from prosthesis delivery to one year.

The investigators propose to utilize a standardized digital stereotactic photography setup (Canfield Dental Camera, Canfield Imaging Systems, Fairfield, NJ) (Fig. 3) from the date of abutment/restoration delivery, and subsequently at 1, 3, 6, and 12 months to accurately document the dynamics of the facial soft tissue. Use of standardized stereotactic digital photography will enable greater accuracy and precision with regard to soft-tissue zenith measurements over time (Fig. 4). This technique is currently being employed as part of a Dentsply Implants-sponsored prospective, randomized, multicenter study called “PROOF” (YA-OSS-0003). After photographic documentation is completed for all time points, a digital software analysis program such as NIH Image J (National Institutes of Health, Bethesda, MD) can be utilized to measure length changes at the mid-facial gingival crest to any desired scale (i.e., tenths of a millimeter or pixels). At recall visits, bucco-lingual peri-implant mucosal thickness will be measured from a fixed reference point, as well as other clinical parameters that include: Plaque Index (PI), Gingival Index (GI) (10), probing pocket depth (PPD), bleeding on probing (BOP) and keratinized mucosa width (KMW) using a UNC-style probe (Fig. 6). These data will be used along with the photographic data to extrapolate the potential role that concavities in the abutment transition zone may play in preserving or enhancing facial soft tissue dynamics.

FIGURES:

[figure not shown]

Fig 6a Mesiodistal section of FM group implant.

Fig 6b Mesiodistal section of CMG group implant.

Fig 6c Mesiodistal section of SA group implant.

(Fig. 1) Histological sections of FM (Fig. 6a), CMG (Fig. 6b), and SA (Fig. 6c) transmucosal profiles, demonstrating superior quantity of connective tissue for CMG configurations.

(Fig. 2) Proposed configurations of the submucosal transition zones of either linear divergent (left) or concave (right) Atlantis™ abutments. Relative lengths of either the divergent (Ld) or concave (Lc) can be calculated

[figure not shown]
during the design/manufacturing process. The volumetric space (x) provided for by the experimental concavity can also be extrapolated from the Atlantis™ software.

(Fig. 3) Canfield Dental Camera (Canfield Imaging Systems, Fairfield, NJ) setup. The patient is oriented in a repeatable position via a bite registration jig and a semicircular camera dial that enables recording of the gingival zenith position at a specific angle between 0-180 degrees.

(Fig. 4) Example of stereotactic digital photographic documentation of a single tooth implant restoration at site #7 using the Canfield Dental Camera (Canfield Imaging Systems, Fairfield, NJ). Such standardized photographs enable precise measurements in the change of the mid-facial soft tissue.

(Fig. 5) Graphical representation of clinical trial Phases 1 and 2. Phase 2 represents the protocol synopsis for the proposed Investigator Initiated Study (IIS). The intent is for 60 patients to be recruited via invitation from Phase 1 (Ridge Preservation RCT) to the Phase 2 portion to optimize completion of the study.

	Visit	1	2	3	5	6	7
	Visit Description	Screening	Implant Placement (IP)	Follow-up	Final Impression & Ostell ISQ	Permanent Crown	Recall Visit
	Visit Window		IP	IP + 2w	IP + 8w	IP + 12w ( $\pm 5$ days)	IP + 1, 3, 6, 12m
Selection process	Informed Consent	X					
	Medical/Dental history	X					
	Oral examination	X					
	Inclusion/exclusion criteria	X					
	Radiographic examination	X (From previous records, if available)		X (optional)			
Study outcomes	Implant Stability		X		X	X	X
	Canfield Photographs					X	X
	Clinical Photographs					X	X
	Bucco-lingual soft-tissue thickness					X	X
	Condition of peri-implant mucosa	PI, GI, PPD, BOP					X
	Adverse Events/Adverse Device Effects		X	X	X	X	X

(Fig. 6) Proposed study plan

**Statistical methods** (Describe where relevant the statistical methods to be used, the populations to be analysed (e.g. determination of sample size, intention to treat, per-protocol), and any interim analyses)

A unified repeated measures analysis (11,12) will be used to describe the time course and to assess the effects of divergent vs. concave abutment design. This approach will make it possible to take into account the correlation of repeated measures on a given subject over time, and to consider the impact of abutment type, as well as other potential covariates. Subject will be treated as a random effect and other factors as fixed effects. Candidate covariate effects that will be explored include sex, age, history of periodontal disease, tooth position, clinical crown anatomy and the condition of adjacent teeth. So as not to exceed the limitations of sample size, we will first consider the relationship of each candidate with the outcome separately, and incorporate those with promising relationships into subsequent modeling. Parameters will be estimated using restricted maximum likelihood

(REML) methods, and a variety of different variance-covariance structures will be entertained, as appropriate. These approaches can accommodate missing data and possible time-dependency of the covariate, both of which may be relevant to this situation. Appropriateness of assumptions associated with the modeling, such as normality, will be fully assessed, and normalizing transformations considered as appropriate. Should these approaches not appear feasible, nonparametric methods for longitudinal data (13, 14) will be considered.

Comparisons of tissue alterations between the two abutments types at each follow-up time are also of interest: Changes relative to baseline will be compared at each of the four recall time points, initially using either the two-sample Student's t-test to compare abutment types, or its nonparametric analog, the Wilcoxon rank sum test, as appropriate. In addition, standard linear modeling will be used to incorporate the possible impact of other covariates. Adjustment for multiple comparisons will be made using the modified Bonferroni method due to Holm (15) in conjunction with an overall Type I error of 0.05.

Analysis of the quantitative secondary outcomes (e.g., keratinized mucosal widths) will be analogous to that for the primary outcome. In addition, we will also characterize the longitudinal course with respect to the categorical outcomes constituting the clinical periodontal evaluations, with initial emphasis being placed upon transition approaches.(12) These will be considered descriptively in terms of the complete three- or four-point ordinal scales, but specific attention will also be given to shifts from clinically acceptable to clinically unacceptable designations. (16,17)

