**Outcome variables**

- Apico-coronal changes of the peri-implant mucosal zenith from prosthesis delivery to one year (Primary).
- Submarginal bucco-lingual soft tissue thickness in the peri-implant transition zone relative to a fixed reference point.
- Quantification of the topographical and volumetric features of the interface between the peri-implant mucosa and the transition zone.
- Keratinized mucosa width in an apicocoronal direction at the midfacial aspect of the implant site.
- Gingival Index (GI), Plaque Index (PI), Bleeding on probing (BOP) and probing pocket depths (PPD) at six sites (disto-lingual, mesio-lingual, mid-lingual, mesio-buccal, disto-buccal, mid-buccal).

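### No masking of the photograph reader to arm or visit is described for the primary endpoint, although coded reading looks feasible at little cost

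*Combined protocol and SAP*

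**What the plan says.** The Outcome variables section of the protocol lists as primary "Apico-coronal changes of the peri-implant mucosal zenith from prosthesis delivery to one year (Primary". Materials and method repeats this: "The primary outcome of the study will be the apico-coronal change of the peri-implant mucosal zenith from prosthesis delivery to one year".

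Materials and method gives the measurement in outline. Photographs are taken at delivery and at 1, 3, 6 and 12 months. The reading follows: "After photographic documentation is completed for all time points, a digital software analysis program such as NIH Image J" is to be used, and such a program "can be utilized to measure length changes at the mid-facial gingival crest to any desired scale (i.e., tenths of a millimeter or pixels". The reader, the number of readers, the landmarks, the reading order and reader repeatability are not given.

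The safeguard described is positional. The Fig. 3 legend says "The patient is oriented in a repeatable position via a bite registration jig", with a camera dial that fixes the angle.

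On what separates the arms, Materials and method refers to changes "induced by the formation of a submucosal concavity" and says the control design is modified "to obtain an abutment that will otherwise retain all the features of the control abutment".

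Masking or blinding of subject, clinician, photograph reader or statistician is not mentioned in any visible section. That covers Study design, Materials and method, Statistical methods and the report of October 2019.

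**The concern.** A standardised camera reduces error from head position and angle. It does not hide the subject, the arm or the visit from the person who decides where the zenith lies. A plan followed as written would therefore allow the primary reading to be made by someone who knows the allocation. The background in Materials and method leans towards the concave design, so a reader's expectation could plausibly differ by arm.

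A systematic reading tendency that differs by arm enters the treatment comparison directly, and a larger sample does not remove it. The changes being measured are small: mean change from delivery is 0.15 to 0.24 mm in either arm (Table 24). A modest tendency could therefore matter for the sign and nominal significance of the result. Here the usual obstacles to masking seem to be absent.

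**Working it through.** **1. The plan's own figures.** Inputs from Power considerations: 25 completers per arm, difference 1 mm, alpha 0.05 or 0.0125. A two-sided two-sample t-test is assumed, because sidedness is not stated. The noncentrality is 1/(SD × √(2/25)), which is 5.05 for SD 0.7 and 3.54 for SD 1.0, with 48 degrees of freedom.

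| SD (mm) | alpha | Stated power | Recomputed |
|---|---|---|---|
| 0.7 | 0.0125 | at least 99% | 99.1% |
| 1.0 | 0.05 | 93% | 93.4% |
| 1.0 | 0.0125 | 82% | 82.2% |

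The figures reproduce. Masking would not change n, alpha or these powers, so the point concerns bias, not sample size.

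**2. The reported 12-month result.** Inputs from Table 24: concave -0.174 (SD 0.278, N 29), divergent -0.238 (SD 0.362, N 25). The table shows no unit, and mm is assumed.

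- Difference, concave minus divergent: -0.174 + 0.238 = 0.064 mm.
- Pooled SD: √[(28 × 0.278² + 24 × 0.362²)/52] = 0.320 mm.
- SE: 0.320 × √(1/29 + 1/25) = 0.087 mm. Unpooled: √(0.278²/29 + 0.362²/25) = 0.089 mm.
- 95% CI with pooled SE: 0.064 ± 0.175, or -0.111 to 0.239 mm; p = 0.47, unadjusted. The report's model gives p = 0.613 for treatment (Table 27).

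The same subtraction at 1, 3 and 6 months gives 0.024, 0.025 and 0.036 mm.

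**3. Illustration of an arm-related shift.** The shift b is an assumption, because the documents give no value. With no true difference, the chance of nominal two-sided significance at 0.05 is the power of the t-test at a difference of b, with noncentrality b/SE. For b = 0.10, the planned case with SD 0.5 has SE = 0.5 × √(2/25) = 0.141 and noncentrality 0.71. The reported case has 0.10/0.087 = 1.15.

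| Assumed b (mm) | Planned 25 per arm, SD 0.5 | Planned 25 per arm, SD 0.7 | Reported Ns, SD 0.32 |
|---|---|---|---|
| 0.05 | 6.4% | 5.7% | 8.7% |
| 0.10 | 10.7% | 7.9% | 20.3% |
| 0.15 | 18.0% | 11.5% | 39.3% |
| 0.20 | 28.3% | 16.8% | 61.4% |

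**4. Effect on the reported difference.** Removing an assumed 0.10 mm shift in one direction gives 0.064 - 0.10 = -0.036 mm (95% CI -0.211 to 0.139). In the other direction it gives 0.164 mm (-0.011 to 0.339). The sign can change. Neither interval comes near 1 mm: hiding a true 1 mm difference would need a shift of at least 1 - 0.239 = 0.76 mm beyond the upper limit.

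**5. Feasibility.** By design the arms differ only beneath the mucosa, so a coded facial photograph should not identify the arm. Reading starts once all time points are complete, so all images of a subject can go into one shuffled list. The number of images is 54 subjects × 5 visits = 270.

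**The case against.** The strongest reply is that silence is not evidence. The protocol is a short synopsis, and the reader may well have been masked. This stands, and the point is limited to what is not described.

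A second reply is that if the photograph does not show the arm, arm-related bias requires a reader who knew the allocation from elsewhere. No section shows that. This also stands, but it does not remove the need to hide the subject's identity: at a single centre, a reader of uncoded files could know who received which abutment.

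A third reply is that the result is null and far inside the 1 mm margin. That limits the consequence for the completed trial. It does not settle the matter, because a shift can also shrink a difference.

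Some stronger readings are tempting but unsupported:

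- A reader might infer that visit order was in view. Table 1 gives an absolute length at each visit, and the Baseline-adjusted Analysis section obtains change by subtraction, which fits image-by-image reading.
- A reader might infer that a drift by visit produced the time effect in Table 13. An assumed 0.10 mm drift would be 42% to 66% of the mean changes (0.10/0.238 and 0.10/0.152), and a drift common to both arms cancels in the arm comparison.
- A reader might treat 0.1 mm as the reading unit and call the arm differences unmeasurable. The protocol names that scale only as an example, and Tables 1 and 24 carry minima and maxima to 0.01 mm.
- A reader might say the protocol states a directional hypothesis. The background favours concave abutments, but the stated hypothesis and primary objective give no direction.
- Manual point placement is likewise an inference from the software named.

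**Conclusion.** The omission is real: masking of the photograph reader to arm or visit is not described for the primary endpoint, and the design makes it easy to provide. Whether the reading was in fact unmasked is unknown.

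The size rests on an assumed shift. At 0.10 mm and no true difference, nominal type I error would be about 11% as planned (SD 0.5 mm) and about 20% at the reported Ns and spread. Against the reported 0.064 mm, such a shift matters for sign and nominal significance, but not for the conclusion about 1 mm. The documents give no evidence that reader bias occurred. This is a cheap improvement worth making; it does not overturn the reported result.

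**What to change.** Add to the photographic measurement paragraph in Materials and method:

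- Each Canfield image gets a random code that hides subject, arm and visit.
- Images are measured in shuffled order against one predefined reference point.
- Codes are linked to allocation only after the readings are locked.
- The same reader repeats a random 10-20% of images under new codes (27 to 54 of 270), and within-reader error in mm is reported beside the primary result.

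For the completed trial, state in the report whether the readings were masked, and how. If they were not, re-read the roughly 270 stored images in this way.

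The cost is file renaming, a shuffled list and a few hours of reading time. No visit or procedure is added, and sample size, alpha and power stay as planned.

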### Study population

*(Short description of target population and indication studied, including relevant criteria for exclusion/inclusion)*

We propose to invite 60 patients participating in a RCT at The University of Iowa College of Dentistry, beginning early/mid 2013 on the efficacy of alveolar ridge preservation ([name] – Principle Investigator). If necessary, additional patients requiring a single-tooth implant (with the same inclusion/exclusion criteria proposed below) will be recruited.

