### Average Keratinized Mucosa Width

### Statistical Analyses

We used mixed models to analyze the effect of time and treatment on each of the variables of interest. The results are summarized in tables below.

Canfield values, bleeding on probing, plaque index, gingival index, and keratinized mucosa width changed significantly over time. Canfield values, bleeding on probing, plaque index, and keratinized mucosa width have a curved relationship with time. Treatment alone is not significant in any model, but is significant in

an interaction with time in bucco-lingual thickness; the effect of treatment on this measure is significantly different across time points.

Table 13: Canfield Model

	P-Value
Time	< .001
Time 	< .001
Treatment	0.853

Table 14: Probing Depth Model

	P-Value
Time	0.096
Treatment	0.307

Table 15: Bleeding on Probing Model

	P-Value
Time	0.0791
Time 	0.0282
Treatment	0.9170

Table 16: Plaque Index Model

	P-Value
Time	0.1640
Time 	0.0436
Treatment	0.9880

Table 17: Gingival Index Model

	P-Value
Time	0.00146
Treatment	0.40900

Table 18: Bucco-Lingual Thickness Model

	P-Value
Time	0.0744
Time 	0.1440
Treatment	0.6740
Treatment:Time	0.0169
Treatment:Time 	0.0359

Table 19: Keratinized Mucosa Width Model

	P-Value
Time	< .001
Time 	< .001
Treatment	0.106

Over time, there was not a significant relationship between bucco-lingual thickness and any of Canfield values, probing depth, bleeding on probing, or keratinized mucosa.

Table 20: Canfield and Bucco-Lingual Thickness

	P-Value
Time	< .001
Time 	< .001
Thickness	0.178

Table 21: Probing Depth and Bucco-Lingual Thickness

	P-Value
Time	0.0928
Thickness	0.6720

Table 22: Bleeding on Probing and Bucco-Lingual Thickness

	P-Value
Time	0.1190
Time 	0.0381
Thickness	0.7340

Table 23: Keratinized Mucosa Width and Bucco-Lingual Thickness

	P-Value
Time	< .001
Time 	< .001
Thickness	0.705

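### Subjects were to come from a randomised ridge-preservation trial, but that allocation is not a listed covariate, covariates are chosen by outcome screening, and no covariate-adjusted model is reported

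*Combined protocol and SAP*

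**What the plan says.** **Source of subjects.** The protocol's Study population section states: "We propose to invite 60 patients participating in a RCT at The University of Iowa College of Dentistry". It keeps a fallback: "If necessary, additional patients requiring a single-tooth implant (with the same inclusion/exclusion criteria proposed below) will be recruited". Materials and method describes the source as "subjects participating in a funded, randomized, controlled clinical trial at The University of Iowa College of Dentistry on the efficacy of alveolar ridge preservation", and the caption to Fig. 5 gives the intent that 60 patients be "recruited via invitation from Phase 1 (Ridge Preservation RCT) to the Phase 2 portion". Abutment design is randomised after implant placement and before final impressions. The method of randomisation is not described.

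**Covariates.** Statistical methods lists six candidates: "Candidate covariate effects that will be explored include sex, age, history of periodontal disease, tooth position, clinical crown anatomy", plus the condition of adjacent teeth. Each is to be related to the outcome separately, and those that look promising go forward into the repeated-measures model. For the comparisons of change at the four recall visits, the section adds without any condition that "standard linear modeling will be used to incorporate the possible impact of other covariates".

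**What was reported.** The statistical report states: "We used mixed models to analyze the effect of time and treatment on each of the variables of interest". Tables 13 to 19 and 27 to 29 contain terms for time, time squared, treatment and treatment by time only. Tables 20 to 23 have time terms and bucco-lingual thickness, which is itself an outcome. The only adjustment is subtraction of the baseline value for three variables (Baseline-adjusted Analysis, Tables 24 to 29).

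**The concern.** Phase 1 allocation is a treatment given to the same site before the implant is placed, and it is known for every subject who came through Phase 1. It is an obvious candidate to explain some of the later soft-tissue change. If it does, leaving it out keeps that variance in the error term and leaves any chance imbalance between the concave and divergent groups in the estimate.

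The selection rule adds a second weakness. With about 27 subjects per group, screening candidates one at a time against the outcome picks covariates partly by chance. It also makes the final model depend on the data, and it can pass over a factor that belongs in the model by design.

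Third, the covariate-adjusted recall-visit models were planned unconditionally and do not appear. The report gives no screening result, no table of the candidates or of Phase 1 allocation by abutment group, and no reason for the omission. A reader can neither check balance nor see what adjustment would have done.

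**Working it through.** **1. The plan's own figures.** Power considerations gives 93% power at alpha 0.05 and 82% at 0.0125 for a 1 mm difference, SD 1.0 mm and 25 per group. A two-sided two-sample t-test (48 df) gives 93.4% and 82.2%, so both reproduce. Neither involves a covariate, so this point does not disturb the sample size.

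**2. Observed primary contrast at 12 months (Table 24).** Concave: mean -0.174, SD 0.278, n = 29. Divergent: mean -0.238, SD 0.362, n = 25.
- Difference = -0.174 - (-0.238) = 0.064 mm.
- SE = sqrt(0.278²/29 + 0.362²/25) = 0.089 mm (pooled: SD 0.320, SE 0.087, 95% CI -0.11 to 0.24, p = 0.47).

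**3. Chance imbalance in Phase 1 allocation.** Assumed: a binary factor split 50:50, all 54 subjects from Phase 1, and abutment randomisation not stratified by it.
- SD of imbalance = sqrt(0.25 × (1/29 + 1/25)) = 0.136, or 13.6 percentage points.
- P(20 points or more, either way) = P(|Z| ≥ 0.20/0.136) = about 14%. If exactly 27 of the 54 are in each Phase 1 arm, the hypergeometric calculation gives 10%.

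**4. Effect on the contrast and its precision.** Let b be the Phase 1 effect on 12-month zenith change. The documents give no value, so b is assumed. Shift = 0.20 × b. Variance share = b² × 0.25 / 0.32². SE ratio, unadjusted to adjusted, = 1/sqrt(1 - share).

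| Assumed b (mm) | Shift at 20 points (mm) | Variance share | SE ratio |
|---|---|---|---|
| 0.1 | 0.02 | 2.4% | 1.01 |
| 0.2 | 0.04 | 9.8% | 1.05 |
| 0.3 | 0.06 | 22% | 1.13 |

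The SE ratio applies when the factor is balanced. With a 20-point imbalance the two factors correlate at about 0.2, which gives back 1/sqrt(1 - 0.04) = 1.02 of the gain. An assumed b of 0.5 mm would need 61% of the change variance (0.0625/0.1024), which is hard to credit, so it is left out of the range.

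**5. Does it matter against 1 mm?** Shifting 0.064 by ±0.06 gives 0.004 to 0.124 mm. Even with the unadjusted SE, the upper 95% limit at 0.124 is 0.124 + 2.01 × 0.089 = 0.30 mm.

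**6. The delivery value as a covariate for thickness.** At 12 months the change scores have SD 1.250 (concave) and 1.036 (divergent) in Table 25. The raw values have SD 0.500 and 0.765 in Table 11.
- SE of the contrast from changes: sqrt(1.250²/29 + 1.036²/25) = 0.311 mm.
- SE of the contrast from raw values: sqrt(0.500²/29 + 0.765²/25) = 0.179 mm.
- Ratio: 0.311/0.179 = 1.74.

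The implied correlation between delivery and 12 months is (s0² + s12² - s_change²)/(2 × s0 × s12), with s0 of 1.129 in both groups. It is about -0.03 for concave and 0.46 for divergent (approximate, because two subjects per group have a delivery value but no 12-month value). With correlations this low, subtracting the delivery value adds noise. Using it as a covariate does not. For the zenith the opposite holds: change SDs of 0.278 and 0.362 against raw SDs of 1.167 and 1.258 (Table 1), so subtraction already does most of the work there.

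**The case against.** The strongest reply is that abutment type is randomised after implant placement, so Phase 1 treatment is a pre-randomisation variable. The unadjusted contrast is unbiased in expectation, and its standard error already allows for chance imbalance. This stands. A reader might infer that the primary comparison is confounded by the earlier trial, and the documents do not support that.

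Two other strong readings also fail. A reader might infer that the trial did not stratify by Phase 1 arm. The protocol is silent on the randomisation method, which does not show that stratification was absent. A reader might also see a self-contradiction, because the protocol says of grafts in a cited retrospective study: "This treatment factor introduces an additional variable that complicates the analysis due to multiple co-variables being present simultaneously". That study had no control group, and the grafts were placed on the facial aspect at provisionalisation, so graft and abutment effects could not be separated. Here there is a concurrent randomised comparator, and the earlier treatment belongs to a separate phase.

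It is also fair to say that the outcome is change from delivery, so stable level differences from ridge treatment drop out and only an effect on later change counts. The covariate list is worded as open. Entry into the mixed model was conditional, so an empty final set was possible under the plan. The number of subjects actually drawn from Phase 1 is not reported.

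What survives is that nothing shows Phase 1 allocation was considered, the screening is not reported, and the covariate-adjusted recall-visit models were planned without the screening condition and are missing.

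**Conclusion.** The point holds as one of precision, chance imbalance and incomplete reporting of the plan. For the primary outcome the stake is small: under assumed Phase 1 effects of 0.1 to 0.3 mm, a shift of 0.02 to 0.06 mm at a 20-point imbalance and a standard error about 1 to 13% larger than needed. Such a shift could rival the observed 0.064 mm, but it comes nowhere near 1 mm, so the primary conclusion is unlikely to change. These figures rest on an assumed effect, an assumed 50:50 split and all subjects coming from Phase 1, none of which the documents settle.

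For thickness the covariate question has more practical weight. The report's only treatment-related finding is the thickness interaction, with p-values of 0.0169 and 0.0359 in Table 18, and 0.0465 and 0.0510 after baseline subtraction in Table 28. Results this close to 0.05 may depend on how the delivery value is handled. The documents do not show which way an adjusted model would go.

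**What to change.** 1. Tabulate Phase 1 allocation by abutment group, including the number of subjects recruited from outside Phase 1.
2. In the primary and thickness models, replace outcome screening with a fixed covariate set: delivery value, Phase 1 allocation and tooth position. If the level for subjects from outside Phase 1 is very small, pool or omit it.
3. Report the adjusted 12-month contrast with its 95% CI beside the unadjusted one, labelled post hoc.
4. Report the covariate analyses that Statistical methods planned, with the screening results, or state why they were dropped.

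The cost is a few degrees of freedom and a merge with Phase 1 records. Those records belong to a trial at the same institution, but access to them is assumed. Items 3 and 4 need no new data collection if the candidate covariates were recorded.
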